## **VI. Informed Consent**

Written informed consent will be obtained from each subject at entry into the study. Consent will be obtained by the research coordinator, and not the subject's physician. Potential subjects will be reassured that choosing not to participate will not jeopardize their medical care. Informed consent is obtained by the following process:

1. The subject (If applicable, parent/guardian) will be asked to review the study consent form.
2. The research coordinator will meet with the subject to review the form, to confirm the subject's understanding of the study, and to answer any questions that the subject might have. The subject will have the opportunity to meet with one of the study investigators, who reviews the eligibility criteria.
3. Once the subject demonstrates understanding of the study and agrees to participate in the study, the consent will be signed in the presence of the research coordinator and a witness.

## **VII. Reporting Changes in Study Status**

During the funding of this study, any action by the IRB or one of the study investigators that results in a temporary or permanent suspension of the study will be reported to the NIH Program Official within 1 business day of notification.

## Appendix A

### DSMP Study Report Figures/Tables

#### Figure or Table 1. Quarterly Enrollment and Randomization

A graph or table will depict quarterly enrollment.

Quarter	# Consented/ Enrolled	# Excluded (and reasons for excluding and ineligibility)	# Randomized	# Not Randomized
2020 Q3 (Jul-Sept)				
2021 Q1 (Jan-Mar)				
Total				

#### Table 2. Demographics

Characteristics	Enrolled Participants	Randomized Participants
Age, years		
Mean (SD)		
Minimum		
Maximum		
Sex, N (%)		
Male		
Female		
Ethnicity, N (%)		
Hispanic or Latino		
Not Hispanic or Latino		
Unknown		
Race, N (%)		
American Indian or Alaska Native		
Asian		
Native Hawaiian or Other Pacific Islander		
Black or African American		
White		
More than one race		
Unknown or Not Reported		
Taking Insulin at Baseline Visit, N (%)		
No		
Yes		
Type of Diabetes, N (%)		
Type 1 Diabetes		
Type 2 Diabetes		
Other		

**Table 3. Subject Status and Class Attendance for Randomized Participants**

Pt Identifier	Date Enrolled (Consented)	End of Trial Date	Study Status (Active or Inactive)	End of Trial Status (Completed, Withdrew, or Lost to Follow Up)	Total No. of Classes Attended (Max 10)	Total No. of Classes and Boosters Attended (Max 14)	Class Attendance/Adherence (%)	Class and Booster Attendance/Adherence (%)

% Adherence to Intervention:

Note: % Adherence will be determined:

- (1) when the first 10 classes the subject is assigned to ends: (#sessions attended/10)\*100
- (2) when all 14 of the sessions the subject is assigned to ends: (#sessions attended/14)\*100

**Table 4. Study Visit Attendance for Randomized Participants**

Quarter	Pt Identifier	Date Enrolled (Consented)	End of Trial Date	Study Status (Active or Inactive)	End of Trial Status (Completed, Withdrew, or Lost to Follow Up)	Reached for 4-week Phone Call	Attended 2-month study visit	Attended 6-month study visit

**Table 5. Out-of-Range Patient-Reported Safety Assessments in Enrolled Participants**

Pt ID	Visit #	9th item of PHQ-9 (Report if $\geq 1$ )	Full PHQ-9 (Report if $\geq 10$ )	GAD-7 (Report if $\geq 10$ )	Higher Risk for Suicide Based on Modified P4 Screener? (Yes, No, or Not Applicable)

**Table 6. Adverse Events in Enrolled Participants**

Pt Identifier	AE # for Pt	SAE (Yes or No)	Adverse Event/ CTCAE Term	Other Term	CTCAE Grade	Do-main	Start Date	Stop Date	Related to Study Intervention	Action Taken	Out-come	Ex-pected

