## **8.0 Subject Numbers and Statistical Plan**

### **8.1 Number of Subjects**

The number of subjects expected to be enrolled and screened is no more than 520 subjects in order to reach the randomization target of 290 subjects. To assure reaching the study's planned sample size requirement (of 290) we will randomize no more than 320 subjects in total.

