## **10.0 Risks**

### Risks of Stress Reduction Programs

*Meditation-related risks:* NCCIH states that meditation is generally safe for healthy people, but that adverse effects have also been reported (NCCIH, 2018). Undesirable side effects and risks of meditation have been

documented in more than 40 scientific reports [for reviews see (Lindahl et al., 2017; Lustyk et al. 2009; Kuijpers et al., 2007; Baer et al, 2019; Britton, 2019; Van Dam et al., 2018)] and are listed in Mindfulness-Based Program Guidelines (Kuyken et al., 2012; Santorelli et al., 2017). More common, less serious side effects that have been reported by individuals within the context of mindfulness-based interventions (MBIs) or who are meditating less than an hour of daily practice include: increased depression, anxiety or panic, re-experiencing of traumatic memories, dissociation, executive dysfunction, headaches/body pain and insomnia (Lindahl et al., 2017; Lomas et al., 2014; Cebolla et al., 2014; Brooker et al., 2013; Johnson et al., 2016; Reynolds et al., 2017; Britton et al., 2010). A few case reports of more serious side effects including mania, psychosis, and suicidality have been reported, mostly in the contexts of intensive retreats (>5 hrs/day) or in conjunction with pre-existing psychopathology (Lindahl et al., 2017; Kuijpers et al., 2007; Kuyken et al., 2012; Yorston, 2001). The frequency of serious adverse effects in the context of MBIs is estimated to be less than 1%, although adequate estimates are not available (Wong et al., 2018). The frequency of non-serious Adverse Events with mild-moderate impairment in functioning is unknown; available estimates range from 1-25% (Baer et al., 2019).

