- e) Description of SAE (CTCAE term) (The research coordinator will enter a symptom, condition/diagnosis (if available), or procedure as the primary event. If a condition/diagnosis has not been identified, the symptom (e.g., chest pain) will be entered, and the event will be updated to the condition/diagnosis when available [e.g., Cardiac Arrest]).
- f) Unexpectedness (1 = Yes, 2 = No) (Refer to List of Previously-Reported Meditation Effects in Appendix C2 and Diabetes Domain Expected Events in Appendix D).
- g) Age of subject (at time of onset)
- h) Sex of subject
- i) Brief description of the nature of the SAE (with no personal identifiers)
- j) Category of SAE (Death with date of death, Life threatening, Hospitalization-initial or prolonged with admission date and discharge date, Disability/incapacity, Congenital anomaly/birth defect, Required intervention to prevent permanent impairment, or Other: \_\_\_\_\_)
- k) Relatedness (using the Relatedness Criteria Definitions Table above in section IV-C and the List of Previously-Reported Meditation Effects in Appendix C2). (Unrelated [clearly not related to the intervention], Possible [may be related to intervention], Definite [clearly related to intervention]).
- l) Whether study intervention was discontinued due to the event? (Yes or No or N/A – event occurred prior to start of study intervention)
- m) What medications or other steps were taken to treat the SAE? \_\_\_\_\_
- n) Intervention type (Medication or nutritional supplement, Device, Surgery, Behavioral/lifestyle)
- o) List any relevant tests, laboratory data, and history, including preexisting medical conditions: \_\_\_\_\_
- p) Is this the final report? (Yes or No)

E.1 Adverse events will be assessed according to the measures and schedule described in the table below.

Name of measure	Visit # 1 Baseline	Visit #2 Follow-up Phone Call after Class #4 (Middle of 8-wk MBSR/SME)	Visit #3 2-month (End of 8-wk MBSR/SME)	Visit #4 6-month (After Booster session #4/End of Study)
PHQ-9	x		x	x
Stress Experience Survey*	x	x	x	x
Subject initiated (passive monitoring)	Ongoing			
Dropout-reason form	Ongoing, as dropouts occur			
*The Stress Experience Survey, includes questions about the most common meditation-related symptoms and other stress related symptoms. These questions may result in the participant reporting an AE. If this occurs, the AE will be marked as "expected" and compared to Baseline and previous visit responses for proper documentation.				

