**E.3.2 Hypoglycemia Survey.** The research coordinator will administer a Hypoglycemia Survey at the baseline study visit, follow-up phone call after Class #4, 2-month study visit, and 6-month study visit. The Hypoglycemia Survey will ask about self-reports of Level 2 hypoglycemia (glucose < 54 mg/dL) and Level 3 hypoglycemia (hypoglycemia requiring the assistance of another person for treatment). Level 2 hypoglycemia will be recorded as an Adverse Event. Level 3 hypoglycemia will be recorded as a Serious Adverse Event.

**E.3.3 Subject Initiated (Passive monitoring):** Subjects are encouraged to contact their instructors and/or study staff if any physical or mental health symptoms arise or other study-related problems occur. Subjects may report AEs at any time throughout the study. Events will be evaluated with the Adverse Events Form by study staff.

**E.3.4 Attrition:** Reasons for attrition are also an important source of AEs. The research coordinator will collect attrition information for each dropout from the study, record the dropout date, subjects' responses to Yes/No questions about general reasons for attrition that do not reveal the subjects' group assignment, and whether the dropout is Subject-initiated or Investigator-initiated.

If it is a Subject-initiated dropout or a lost to follow-up, the subject will be e-mailed a link to a REDCap Participant-Completed Attrition Information Survey consisting of one open ended question to elicit feedback about their experience in the study and learn more about their reasons for not continuing in the study. As subjects' responses could reveal group assignment, the research coordinator and other blinded study team members will not have access to subjects' responses to this survey in REDCap.

**Investigator-initiated withdrawals:** A subject may also be withdrawn from the study and/or intervention by the investigator. In this case, the research coordinator will record the reasons why the investigator withdrew the subject from the study.

To report data on subject status, adherence/attendance at MBSR or SME classes, and attendance at study visits, we will use Tables 3 and 4 in Appendix A.

To report data on Adverse Events and Serious Adverse Events, we will use Tables 6 and 7 in Appendix A.

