## D. Stopping Rules

This study will be stopped prior to its completion if: (1) the intervention is associated with adverse effects that call into question the safety of the intervention; (2) difficulty in study recruitment or retention will significantly impact the ability to evaluate the study endpoints; (3) any new information becomes available during the trial that necessitates stopping the trial; or (4) other situations occur that might warrant stopping the trial.

The PI will include an assessment of futility in the annual progress report to NIH and will consult with the study monitors and the NIH Program Official to assess the impact of significant data loss due to problems in recruitment, retention, or data collection.

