## **F. Safety Review Plan**

Study accrual, subject retention, subject adherence to intervention sessions, and study safety will be reviewed by the DSMB every 6 months (and more frequently if needed) starting 6 months after randomization of the first study cohort. Progress reports, including patient recruitment, retention/attrition, and AEs will be provided to the Data Safety Monitoring Board following each of the reviews. An Annual Report will be compiled and will include a list and summary of AEs. In addition, the Annual Report will address (1) whether AE rates are consistent with pre-study assumptions; (2) reason for dropouts from the study (only blinded information; unblinded information from the open-ended attrition item will not be provided); (3) whether all participants met entry criteria; (4) whether continuation of the study is justified on the basis that additional data are needed to accomplish the stated aims of the study; and (5) conditions whereby the study might be terminated prematurely. The Annual Report will be sent to the Data Safety Monitoring Board and will be forwarded to the IRB, NIH, and other applicable recipients who will review the progress of this study on an annual basis.

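### The DSMB's adverse event tables mix pre-randomization events and never-randomized subjects with events after the programs start, and the AE rate to be reported has no defined population, window or denominator

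*Combined protocol and SAP*

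**What the plan says.** DSMP Appendix A sets out the tables the DSMB receives. Tables 3 and 4 (status, class attendance, visit attendance) are limited to randomized participants, and Table 2 shows enrolled and randomized participants side by side. The three safety tables use the wider set. Table 6 is headed "Table 6. Adverse Events in Enrolled Participants", and Tables 5 and 7 are titled the same way. Tables 1 and 3 equate enrollment with consent. Protocol section 8.1 gives the numbers: "The number of subjects expected to be enrolled and screened is no more than 520 subjects", for a target of 290 randomized and a maximum of 320.

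On timing, protocol sections 9.3 and 7.2.4 and DSMP IV.E have AEs recorded at the baseline visit, with randomization only after the baseline measurements. DSMP IV.E.3.2 says: "The research coordinator will administer a Hypoglycemia Survey at the baseline study visit" and at the later contacts. It then says: "Level 2 hypoglycemia will be recorded as an Adverse Event. Level 3 hypoglycemia will be recorded as a Serious Adverse Event". No exception is made for baseline answers and no look-back period is given. The Stress Experience Survey (DSMP IV.E.3.1) is handled differently: an item becomes an AE only if it is more frequent than at baseline or the previous visit.

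On use, DSMP V.F requires the Annual Report to address "whether AE rates are consistent with pre-study assumptions". The only pre-study frequencies in the documents are in protocol section 10.0 and DSMP IV.D. They concern mindfulness-based programs: "The frequency of serious adverse effects in the context of MBIs is estimated to be less than 1" per cent, and 1 to 25% for non-serious events.

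**The concern.** A statement about AE rates is useful to a DSMB only if it is known whose events are counted, from when, and over how many people. None of the three is stated. The tables through which DSMP IV.E.3.4 says AEs and SAEs will be reported cover people who may never enter either program, and events that occurred before either program began.

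The hypoglycemia rule makes this more than a missing detail. Followed as written, it places events from before the intervention, in people with uncontrolled diabetes, into the AE and SAE tables. The same plan treats the other survey's baseline as a reference value.

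The comparator differs in kind too. The tables hold all-cause events, including COVID-19, whereas the pre-study figures describe effects of mindfulness programs. A crude rate could look reassuring because the denominator is too large, or alarming because events preceded exposure, and the report as laid out would not show which.

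**Working it through.** The documents state no AE rate, so there is no safety figure to reproduce. The randomized total, which a post-start rate would use as its denominator, does reproduce from protocol section 8.2 (difference 0.5, SD 0.9, two-sided 0.05, power 80%, design effect 2.36, dropout 15%):

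- Normal formula: 2 × (0.9 × (1.960 + 0.842) / 0.5)² = 50.9, so 51 per arm. Then 51 × 2.36 / 0.85 = 141.6, which gives 142 per arm and 284 in all.
- t distribution: 52 per arm. Then 52 × 2.36 / 0.85 = 144.4, which gives 145 per arm and 290 in all.

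Step 1, the denominator alone. Inputs are 520 enrolled (ceiling) and r = 290 or 320 randomized. If every event falls after randomization, a true proportion p in randomized subjects appears as p × r / 520.

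- r = 290: 290/520 = 0.558. A true 25% reads 13.9% and a true 1% reads 0.56%. The other 230 people (44.2%) are never exposed.
- r = 320: 320/520 = 0.615. A true 25% reads 15.4% and a true 1% reads 0.62%. The other 200 people (38.5%) are never exposed.

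Step 2, adding pre-randomization events. Let b be the proportion of people with a recorded event before randomization, independent of later events. The documents give no baseline hypoglycemia frequency, so b is an assumption and is shown as a range. Two versions bound the case, because people who fail at screening never reach the baseline survey:

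- A, b applies to all enrolled: [r(1 − (1 − p)(1 − b)) + (520 − r)b] / 520.
- B, b applies to randomized subjects only: r(1 − (1 − p)(1 − b)) / 520.

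With r = 290 and p = 25%:

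| Assumed b | A | B |
|---|---|---|
| 0 | 13.9% | 13.9% |
| 5% | 18.2% | 16.0% |
| 10% | 22.5% | 18.1% |
| 20% | 31.2% | 22.3% |
| 30% | 39.8% | 26.5% |

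For example, A at b = 10%: 290 × (1 − 0.75 × 0.90) = 94.25; add 230 × 0.10 = 23; 117.25/520 = 22.5%.

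For a true 1% and b = 5%, A gives 28.755/520 = 5.5% and B gives 17.255/520 = 3.3%.

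Step 3, where the two errors cancel (r = 290).

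- A: b = p(520 − r)/(520 − rp), which is 12.8% for p = 25% and 0.44% for p = 1%.
- B: b = p(520 − r)/(r(1 − p)), which is 26.4% for p = 25% and 0.80% for p = 1%.

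Below these values the table-based rate understates the true one; above them it overstates it. The direction cannot be known in advance.

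Step 4, whether the report lets a reader separate the events. Table 6 has a start date and relatedness, Table 7 has an onset date and relatedness, Table 1 gives the number randomized, and Table 3 lists the randomized identifiers. No Appendix A table carries a randomization or Orientation date, so a start date cannot be placed before or after exposure from the report itself. The option "event occurred prior to start of study intervention" is on the SAE form only, as an answer to the discontinuation item; the AE form has no counterpart.

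**The case against.** Listing every event from consent onward is sound. The DSMP defines an AE by participation in the study, and fasting, blood draws and sensitive questionnaires carry risks before randomization. That stands in full, and the listings should stay.

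Tables 6 and 7 are line listings with dates and relatedness, from which a statistician holding the database could build the right rate. That stands in part: the data exist, but the report neither carries the reference date nor asks for the summary.

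Three stronger readings are tempting and are not supported.

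- A reader might infer that the AE rate is computed over enrolled subjects. The plan does not say so. DSMP V.F names no table, numerator or denominator, so the rate is undefined rather than shown to be wrong.
- A reader might infer that these tables drive the safety stopping ground. That ground, "the intervention is associated with adverse effects that call into question the safety of the intervention", cites no table, rate or threshold and already requires a link to the intervention. Nor do the documents show that a numerical trigger is needed: the DSMB sees SAEs per occurrence, may review more often than six-monthly, and may ask for group-identifiable material.
- A reader might take 520 against 290 as the expected ratio. The 520 is a ceiling and up to 320 may be randomized. Many of those not randomized will leave at screening and contribute few events.

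**Conclusion.** The point holds as a reporting gap. The safety tables cover all consented subjects and include pre-randomization events. Baseline-reported hypoglycemia enters as AEs and SAEs, inconsistently with the plan's handling of its other safety survey. The Annual Report's AE rate is undefined and, if taken from these tables, would not measure events after the programs start.

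At the 520 ceiling the denominator effect is a factor of 0.56 to 0.62. The numerator effect runs the other way and depends on the assumed b; with r = 290, a true 25% could read anywhere from 13.9% to 39.8% for b between 0 and 30%. These sizes rest on the ceiling being reached and, for the numerator, on independence and an assumed b.

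The primary efficacy analysis and per-occurrence SAE review are unaffected. The change is still worth making because the data are already collected. Even a correct post-start rate will not isolate harm from MBSR while the arms are pooled: about half of the randomized subjects receive SME. The documents themselves warn that adequate estimates of serious effects are lacking, so the 1% figure is a loose benchmark and not a limit.

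**What to change.** In DSMP V.F and Appendix A:

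- Keep the listings of enrolled participants and the per-occurrence SAE reporting unchanged.
- Add the randomization and Orientation dates to Tables 6 and 7.
- Add one summary of AEs and SAEs that start or worsen on or after randomization, with randomized subjects as the denominator, and name it as the source of the rate statement in V.F. Randomization matches the denominator; if the first session is preferred as the start, say so.
- Show baseline Hypoglycemia Survey answers, other pre-randomization events and events in non-randomized subjects separately, the first as baseline history.
- Set against the mindfulness-program figures (below 1% serious, 1 to 25% non-serious) only events rated at least possibly related, and note that pooled arms limit the comparison.
- Reconcile protocol section 7.2.4, which has study group data shown to the DSMB in blinded form, with DSMP V.G and Appendix B, which have tables not broken down by group.

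The cost is DSMP and table-shell wording, one added column (two if both dates are shown) and one added summary table. Event dates, relatedness and randomization status are already collected, so no new visits or data are needed.

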**Table 7. Serious Adverse Events (including deaths) in Enrolled Participants\***

Pt Identifier	Link to Pt AE #	Date Pt Reported	Onset Date	Dx Date	SAE Stop Date	SAE Category	Related to Study Intervention	Age at Onset	Description of Actions and Outcomes (e.g., hospitalization, withdrawn from study)

\* Adverse events will be determined to be SAEs based on the Severity Grading Tool (Appendix C1)

SAE Category: Death, Life threatening, Hospitalization-initial or prolonged, Disability/incapacity, Congenital anomaly/birth defect, Required intervention to prevent permanent impairment, or Other: \_\_\_\_\_

Level 3: Severe hypoglycemia, as defined by the ADA denotes severe cognitive impairment requiring the assistance of another person for treatment, will be considered a SAE (Workgroup on Hypoglycemia, ADA, 2005; Sequist et al., 2013).

Relatedness: 0 = Not related, 1 = Unlikely related, 2 = Possibly related, 3 = Probably related, or 4 = Definitely related based on the the Relatedness Criteria Definitions Table above in section IV-C and the List of Previously-Reported Medication Effects (Appendix C2)

**Table 7. Serious Adverse Events (including deaths) in Enrolled Participants (Continued)**

Pt ID	Link to Pt AE #	Date of Death	Hospital Admission Date	Hospital Discharge Date	SAE Other Category	Unexpected	Intervention Discontinued due to SAE?	Treatment of SAE	Tests, Labs, Medical History, Pre-existing Medical Conditions

## **Appendix B**

### **DSMP Study Report Outline for the Data Safety Monitoring Board**

The study team will prepare a study safety report which will begin with a brief introduction section describing the study status, issues, and procedures that produced the report (e.g., data obtained by specific date). A study description with a current timetable and study schedule will be included. Study data reports will describe enrollment, demographic characteristics and safety assessments. Study Report tables will be generated only from aggregate (not by group assignment) baseline and aggregate safety data for the study population.

